7. RECRUITMENT METHODS

Potential participants will be recruited through a variety of mechanisms, consistent with previous studies in our research group and in CIFASD. The Study Website will include information about the study, as well as a link to the study REDCap Consenting and Screening Module for interested families to enroll.

The following materials have been developed to aid with recruitment: (1) study flyers, (2) social media banners formatted for Facebook, Twitter, and Instagram, and (3) powerpoint slide. Information about the study will be disseminated in various ways:

- [name] will share study recruitment materials with providers and community advocates who regularly see children with FASD
- We will post study information on our study Twitter account (@FMFConnect) and newsletter (www.fmfconnect.com)
- CIFASD investigators can inform research participants or patients in their local sites or clinics for which they have routine access
- The National Organization on Fetal Alcohol Syndrome (NOFAS) is a member of CIFASD and has a mission to educate the public about FASD and disseminate research and policy information. They can disseminate the study flyer through their Weekly Round-Up newsletter, significant social media presence, and to their state and local affiliates who can share in their communities
- [name] and other CIFASD investigators may include slides about the study in conference or community presentations
- Organizers/moderators of popular social media groups can be sent recruitment materials and can choose to share with their members

As part of CIFASD, we will also try to aid other projects with recruitment from our study sample. Our Consenting and Screening Module includes a question asking if participants are interested in learning about other studies. For those that indicate yes, we will send them any new relevant flyers or information about other consortium projects they might be eligible for. We will submit any flyers and email language in a modification to this study prior to sending to our participants. For example, the DiG Human Genetics Study within CIFASD has previously referred some families to our study. We would like to send their study flyers (see attached flyer and email language) to participants in our sample who indicated they have not previously done the DiG study (in Screening Module).

8. CONSENT PROCESS

Interested parents/caregivers will go to the Study Website to begin the informed consent process. On the Study Website they will select the link that they are interested in participating. This link will take them to the study REDCap Consenting and Screening Module, hosted at UR. Interested participants will have the option to review study consent information by video or text. They are also told they can contact the study team by phone or email to complete the consent process over the phone/video chat if they prefer (the research team would send them the consent and then go over it by phone/HIPAA-compliant video chat; participant would return signed copy).

- **Text option:** the text of the Consent document will be presented on the screen for potential participants to read. The Consent document will include the HIPAA authorization.
- **Video option:** the animated video reviews key details from the Consent document. The HIPAA authorization, and information about email and texting the research team are presented following the video in text.

For either option, participants will need to answer several questions about the study to ensure comprehension. Participants will also be asked to indicate if they have questions and space will be provided for them to type in any questions they have. If the participant selects “yes” they have questions, they will be informed the study coordinator will contact them before they proceed. The study coordinator’s contact information will also be presented if participants want to contact the coordinator with questions while reading the document. The study coordinator will document contact in the study contact log in REDCap.

If they don't have questions or the coordinator has addressed them, participants can sign the consent form by utilizing REDCap's signature field. Questions asking for first and last name and date of birth are included as extra documentation of the participant's identity. The participant will then select "Next Page" and a read only copy of the consent will be generated that they can review, download, and/or print. At the bottom of the page they will need to select "I certify that all the information in the document above is correct, and I understand that signing this form electronically is the equivalent of signing a physical document." Once this is selected they will be able to submit the signed consent form.

Upon completion of the consent survey, a static copy of their responses in the form of a consent-specific PDF will be stored in the project's File Repository in REDCap (to allow for versioning). The e-Consent Framework in REDCap also records the IP address of the participant and displays this information in the file repository in order to help regulate potential duplicate forms from a single IP address. A PDF file of the completed consent form will be available for download by the user. The PDF can also be emailed to participants or printed/sent to participants in the mail on request if they are unable to open or save a copy electronically on their device.

After completing the consent document, participants will be directed in REDCap to answer screening questions to assess eligibility for the study (see Screening Form). If eligibility criteria clearly aren't met (e.g., out of age range, outside the US, no smartphone, etc), parents/caregivers will be informed immediately that they aren't eligible and the module will end. For parents/caregivers who appear to meet criteria or in cases where parents/caregivers answer "unsure" for any of the questions, contact information will then be gathered. Contact information will also include necessary variables to generate their "globally unique identifier" (GUID), which is used in other CIFASD studies (<https://nda.nih.gov/s/guid/nda-guid.html>).

Common variables are used across several CIFASD studies. We have adapted and streamlined several CIFASD Common Forms for the purposes of this study, which will be administered next in REDCap. These forms include: the Parent Demographic Form, the Child Demographic Form, the Prenatal Exposure History, and the FASD Diagnosis History forms. These forms take about 15 minutes or less to complete in total. After completing the Consenting and Screening module, participants will be notified that project staff will review all submitted information to assess final eligibility.

Participant completion of the study consent document also triggers an automatic notification to the study coordinator, who will log-in to REDCap and review the consent. She will then add her name and date to the eConsent document. However, the date study staff sign the eConsent may differ from that of the participant; for example, if the participant completes the forms on a weekend. The coordinator will also document the date of this review in the study database and download a copy of the consent form to maintain in study records. Next the coordinator will review screening responses and demographic variables to assess eligibility and will document this in the study database. See next section.

This study is funded by the National Institute of Health (NIH). A Certificate of Confidentiality is automatically included as part of the notice of award. Language regarding the Certificate of Confidentiality is included in the consent form.

9. STUDY PROCEDURES

Data Collection & Randomization Procedures

Parents/caregivers who are eligible for the study will be sent an email inviting them to complete the baseline study surveys (see survey battery below) administered by REDCap. Participants will be

asked to enter their zip code to verify their identity when completing baseline and follow-up surveys (this will be verified against value entered in demographic surveys in the screening module). Families deemed ineligible after detailed review will be informed of their status.

Following baseline survey completion, participants will be randomized to one of three arms of the RCT:

1. FMF Connect app + text based coaching (within the app)
2. FMF Connect app (without coaching)
3. Waitlist control

Randomization will occur through the REDCap Randomization module, with an equal allocation pattern across groups. Participants will be notified of their group status via email. Emails for parents/caregivers in either of the FMF Connect app intervention groups (groups 1 and 2) will also include instructions of how to install the FMF Connect app on their devices. The email for the parents/caregivers in the FMF Connect app + coaching group (group 1) will inform them that they will receive an introductory email from their assigned coach in the next few days. Details about the FMF Connect app and Coaching interventions and described below.

All participants regardless of group assignment will receive emails through REDCap at 6 weeks and 12 weeks inviting them to complete follow-up surveys, along with a personalized link (see survey battery below). The assessment battery is estimated to take 35-45 minutes to complete at T1 and T3; T2 is estimated at 15-20 min. Waitlist control participants will receive the FMF Connect app following T3 survey completion.

Measure	Baseline (T1)	6-Weeks (T2)	12-Weeks (T3)
Eyberg Child Behavior Inventory (5-8min)	X		X
Reasons for Children’s Behavior Scale (4-6min)	X	X	X
Everyday Life Scale (4-6min)	X	X	X
Parenting Sense of Competence Scale (3-5min)	X	X	X
Family Needs Questionnaire (3-5min)	X		X
Knowledge & Advocacy Questionnaire (15-20min)	X		X
Self-Care and Support Assessment (3-5min)	X		X
Adverse Childhood Experiences (2 min)	X		
Family Background & Services Survey (5-10min)	X		X
COVID-19 Experiences Survey (5 min)			X
User Version of the Mobile Health Application Rating Scale (5-8min)			X

FMF Connect mHealth Intervention

The FMF Connect intervention includes cloud infrastructure and an innovative, multilayered mobile app. It incorporates tailored content for parents/caregivers of children (ages 3-12) with FASD or PAE. The app integrates five main components: 1) Dashboard; 2) Learning Modules; 3) Family Forum; 4) Library; and 5) Notebook. Weekly emails are also sent to support motivational engagement.

App education, derived from the standard FMF Program, is packaged in easily digestible Learning Modules. The Learning Modules are organized into three levels: 1) Getting Started; 2) Taking Action; and 3) Taking It to the Next Level. The Library provides access to additional optional content that can be downloaded and printed to use in advocacy and skill development. The Notebook is a personalized section that organizes parents’/caregivers’ responses to learning activities in a convenient location for

later easy access.

The Family Forum serves to 1) engage and facilitate parents'/caregivers' continued utilization of the app, 2) support and extend parents'/caregivers' implementation of new knowledge and skills, and 3) provides peer support, encouragement, and understanding of the parent's/caregiver's own needs. Trained peer moderators will moderate discussion in family forums to ensure safety. They will also provide support and prompt skills or content areas to consider.

The Dashboard displays parent/caregiver progress in Learning Module completion, use of the Family Forum, and daily and weekly ratings imputed by the parent/caregiver. It also includes the Tip of the Day feature.

Complementing the app is a Cloud infrastructure to transparently but securely distribute information, including storing and retrieving data, managing notification and messaging, and synchronizing data on all devices. A local datastore will protect the mobile app against network failures and connectivity issues. This local datastore will be transparently synchronized with the Cloud database so that all the querying and security features will be always available regardless of network connectivity. Updates will be automatically pushed out so users have the latest version.

The primary purpose of FMF Connect is to provide parent/caregiver education and support. It does not meet the FDA's definition of a medical device; it is not aiming to cure, treat, mitigate, or prevent FASD and is most similar to apps within the General Wellness category.

Coaching Module

On average, about 25% of apps are only used once after download [14], and only 29% of app users were still using an app 90 days after download [15]. A Coaching Module has been developed within the FMF Connect app to help engage parents/caregivers and support continued use and individualized goal setting within the app.

The Coaching Module will be activated for parents/caregivers in the FMF Connect + Coaching group only. This Module will allow their assigned coach to exchange text-based messages through the FMF Connect app's notification system with them. Coaches will have access to a dashboard of their participants' progress and use of the app, which will aid in tailoring messages and supporting parents in their identified goals. The Coach's interface also provides a secure way to provide text-based messages to the participant within the app.

Coaches include research staff and graduate students on the project who are familiar with the FMF Program principles and are knowledgeable about FMF Connect content and features. They have training in motivational interviewing (MI), which is a key therapeutic technique used in the FMF Program. Coaches will use the spirit and skills of MI to elicit the participant's own motivation to learn more about FASD and skills taught in FMF Connect. They will help align the parent's/caregiver's own values and goals with the content and features within FMF Connect.

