4. STUDY DESIGN

This study involves a three arm RCT with equal allocation to the following conditions: (1) FMF Connect + coaching, (2) FMF Connect alone, and (3) waitlist control. Quantitative survey data will be collected at three timepoints: baseline (T1), 6-weeks (T2), and 12-weeks (T3). The T2 timepoint will involve an abbreviated battery designed to allow statistical tests of mediation hypotheses (see Data Analysis Plan below). Primary study outcomes include child behavior, parent FASD knowledge,

parenting self-efficacy, behavior attributions, family needs met, and parent use of self-care. We are also interested in participant ratings of app quality and patterns of app usage. App usage will be recorded through AWS during the study period. After T3, study participants in the waitlist control group will receive the FMF Connect app.

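### The T3 knowledge questionnaire is answered remotely when only the app arms can open the FMF Connect content, and no safeguard against differential look-up is described

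*Combined protocol and SAP*

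**What the plan says.** Section 4 (Study Design) makes knowledge a primary outcome: "Primary study outcomes include child behavior, parent FASD knowledge", followed by four others. Section 9 (Study Procedures) schedules the Knowledge & Advocacy Questionnaire, "Knowledge & Advocacy Questionnaire (15-20min" in the survey table, at T1 and T3 but not T2.

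On mode of collection, section 9 states: "All participants regardless of group assignment will receive emails through REDCap at 6 weeks and 12 weeks inviting them to complete follow-up surveys". The only control described when a survey is completed is that participants are "asked to enter their zip code to verify their identity when completing baseline and follow-up surveys". Sections 9 and 19 describe no supervision, time limit, request to answer from memory, or question about materials used.

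On access to content, randomization follows the baseline survey, so no arm has the app at T1. From then on the app arms can use the Learning Modules, a Notebook holding their own responses, and a Library: "The Library provides access to additional optional content that can be downloaded and printed to use in advocacy and skill development". For the comparator, "Waitlist control participants will receive the FMF Connect app following T3 survey completion"; section 4 says the same.

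**The concern.** The app's stated primary purpose is caregiver education and support, so its content and the knowledge outcome share a subject. At T3 a caregiver in either app arm can answer with the trial's own teaching material open, and a waitlist caregiver cannot. If some do so, the T3 score reflects retained knowledge plus look-up, and more so in the app arms. Because the asymmetry arises after randomization, neither a change score nor baseline adjustment removes it.

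At stake is how a positive knowledge result is read. A reader could ask whether the app taught caregivers or was simply open when they answered, and the data as planned could not answer. The same mechanism could reach Aim 1, which relates app usage to change in outcomes including knowledge: "App usage will be recorded through AWS during the study period", so a session opened during the survey could raise both usage and score.

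**Working it through.** The plan gives no figure for look-up, so there is none to reproduce. The arithmetic below only shows what an assumed bias would do.

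**Inputs from the documents**
- 150 analysed and equal allocation (sections 19 and 9): 50 per arm, so 100 pooled app v 50 waitlist.
- Correlation among repeated measures r = .3 to .5, alpha = .05 (section 19, Aim 2).
- Two time points for knowledge, T1 and T3 (section 9).

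**Assumed inputs, not in the documents**
- Share q of caregivers who look up answers, and mean gain g in SD units among those who do.
- Equal SD at T1 and T3, and no true effect.

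**Step 1: bias.** The spurious difference is b = (q x g) in the app arms minus (q x g) in the waitlist arm. With no waitlist gain:
- 5% x 0.5 SD = 0.025 SD
- 10% x 1 SD, or 20% x 0.5 SD = 0.10 SD
- 25% x 1 SD, or 50% x 0.5 SD = 0.25 SD

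With equal gain in all arms, b = 0.

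**Step 2: standard error.** Aim 2 specifies repeated-measures ANOVA. With two time points, the pooled app-v-waitlist group-by-time contrast is a comparison of changes, so SE = sqrt(2(1 - r)) x sqrt(1/100 + 1/50), and the second factor is 0.173.
- r = .3: 1.183 x 0.173 = 0.205
- r = .5: 1.000 x 0.173 = 0.173

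**Step 3: rejection rate** (two-sided 5% test, noncentral t, 148 df, noncentrality b/SE).

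| b (SD) | b/SE, r = .3 | Rejects | b/SE, r = .5 | Rejects |
|---|---|---|---|---|
| 0.025 | 0.12 | 5.2% | 0.14 | 5.2% |
| 0.10 | 0.49 | 7.7% | 0.58 | 8.8% |
| 0.25 | 1.22 | 22.8% | 1.44 | 30.0% |

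A baseline-adjusted analysis, with SE factor sqrt(1 - r^2), would give 9.2%-10.2% for b = 0.10 and 32.4%-38.1% for b = 0.25. Those are not the rates for the Aim 2 analysis as written.

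**Step 4: plausibility of the larger case.** Section 5 expects about 80% to install the app and use it at least once. The Coaching Module text in section 9 cites a general benchmark of 29% of app users still active at 90 days. If both applied, 0.80 x 0.29 = 23% of the app arms would be active near T3. A 25% look-up share would then need slightly more than every active user. The benchmark is not specific to this app, coaching is meant to raise use, and an idle app can be reopened for a survey. The 0.25 SD case therefore belongs at the high end but cannot be excluded.

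**The case against.** The strongest case against is that this is conjecture common to any remote knowledge test. The documents do not show the questionnaire's items, format, scoring or instructions, and do not say its items come from app content. A from-memory instruction may already be on the form. Every caregiver answers online and unsupervised, and section 2 notes that many families use peer-to-peer and self-help sources, so look-up in general is open to all arms at both times. Payment (section 13) is for completing surveys, not for scores, so the incentive is weak.

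Most of this stands, and it rules out two stronger readings. A reader might infer that the T3 score does mix knowledge with look-up, and in the app arms only. The documents do not support that: no look-up is reported, and only the FMF Connect content is restricted to the app arms. A reader might also infer that the Aim 1 usage-knowledge association is inflated. That is possible, but one survey-time session may be a small part of 12 weeks of logged use, and nothing in the documents allows its effect to be sized.

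What the objection does not remove is the asymmetry. The trial's own content is available to two arms and not the third when the outcome is measured. Equal gain from other sources cannot be presumed, since section 2 itself says the credibility of such information is hard to evaluate.

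**Conclusion.** The point holds as a low-severity gap: a primary outcome is collected remotely with no described safeguard against look-up, when only the app arms can open the teaching content. Any look-up in that content would favour the app.

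The size of the bias cannot be derived from the documents. The rejection rates of about 8%-9% at 0.10 SD and 23%-30% at 0.25 SD rest on assumed look-up shares and gains, no waitlist gain, no true effect, and the change-type contrast. At 0.025 SD the effect is negligible. Expected non-installation of about 20% dilutes the bias if the look-up share is counted among installers only. The case for acting is that the remedy is nearly free and the information cannot be recovered once T3 is collected.

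**What to change.** At T1 and T3, identically in all arms:
- Add one line to the Knowledge & Advocacy Questionnaire asking caregivers to answer from memory, without the app or other materials. If the form already carries such a line, state so in section 9.
- Add one item asking whether any material was consulted.

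In section 19, report the Aim 2 knowledge comparison with all records as the main result, and again without records of self-declared look-up in any arm, as a sensitivity analysis only.

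Do not exclude records because the AWS logs show an app session shortly before submission, for example within 30 minutes. The measures listed after the knowledge questionnaire at T3 take 18 to 28 minutes (3-5 + 5-10 + 5 + 5-8), so, if the battery follows table order and is submitted together, such a window would miss most of the questionnaire. T3 also includes the app rating scale, which may prompt legitimate opening of the app. The exclusion would be post-randomization and fall on the app arms only. Logs also cannot see printed Library pages. If logs are used, describe sessions that overlap the questionnaire and keep the records in.

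The cost is one line, one item and one extra analysis. The downside is that the sensitivity analysis conditions on post-randomization behaviour and on self-report, so it can support the main result but not replace it.

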10. RISKS TO SUBJECTS

Risks to Subjects

Participants may experience psychological risks associated with participation in this study, such as discomfort or boredom in answering questions or providing feedback about the app. Psychological discomfort is also possible during interactions between participants as part of the Family Forum of the FMF Connect app. This potential risk of discomfort is expected to be similar to other social media use.

There is also a risk of loss of confidentiality. All data collected for the proposed research study will be kept confidential to the extent allowed by law. Although it is unlikely given the nature of this study, if participants disclose that someone is being maltreated or is a danger to self or others, research staff will need to break confidentiality to make a report to the appropriate authority to ensure safety, as mandated by law. The Coaches and Peer Moderators in the Family Forum will be trained to promptly alert [name] if there are concerns about a participant or their family's well-being so she can take appropriate steps, which may include alerting outside authorities to ensure safety. It is also possible that other parents/caregivers in the Family Forum might disclose personal information about other participants who post in the Forum to people outside of the research studies. We believe that all identified risks are reasonable given the proposed procedures for protecting against risk.

Protections Against Risks

To minimize risk associated with psychological discomfort, participants will be given the option to skip questions they feel uncomfortable answering. The Peer Moderators in Family Forum will be trained in creating a welcoming, nonjudgmental, and supportive environment for all participants. Clear rules and expectations will be delineated for the Peer Moderators and participants. Participants will be notified of these rules and expectations upon receiving the FMF Connect app and will be reminded throughout their participation. Any violations of these rules and expectations will be addressed by the Peer Moderators (e.g., removing posts, alerting [name]). These violations will also be reviewed by [name] during supervision with the Peer Moderators. Participants will also have the ability to send an email to project staff if they experience discomfort during their participation in the Family Forum. Appropriate actions will be taken under [name] supervision to address discomfort and participant well-being and safety. Participants can also choose to not enter or post in the Family Forum if they do not feel comfortable or are not interested in this component.

Multiple procedures will be implemented to protect participant confidentiality. In terms of data storage and management, any hard copy data will be secured in locked file cabinets within locked offices, available only to program staff. Electronic data will be stored in secured servers, and only program staff with knowledge of the password will be able to access the data. Forms with identifying information will be separated from the data collected and only subject numbers will be retained in data analysis files.

Multiple levels of protection will be put in place to reduce the risk of loss of confidentiality for data collected through the app. A local datastore will protect the mobile application against network failures and connectivity issues. This local datastore will be transparently synchronized with the Cloud database so that all the querying and security features will be always available regardless of network connectivity. Collected data will be stored using a random code that will not allow direct identification of a particular subject, while any data that identify the user will be stored separately. All the connections between the mHealth app and the Cloud, as well as access and storage to the Cloud database, will use state of the art authentication and encryption algorithms (e.g., HTTS, SSL and TLS). These were built and are managed by [name]. As a result, users will be able to add and modify their own data but will be prevented from viewing and modifying other users' data. FMF Connect will also not alter the security settings of the user's phone, access stored information in the phone, or access device functionalities without explicit user consent. A passcode (or touch ID/Face ID) will be required to access the content of the FMF Connect app, and all the personal data stored by the app will be encrypted automatically whenever the device is locked.

All information obtained for research will be kept strictly confidential (as allowed by law) by research staff. Participants will be told about all exceptions (e.g., child/dependent adult abuse, harm

to self or others) to confidentiality during the consent process. Project staff (which includes Coaches) and the Peer Moderators will be closely supervised by [name] and instructed on confidentiality, including what information is confidential, the limits of confidentiality, and to whom to report concerns. If maltreatment is suspected, staff will first discuss their concerns with the caregiver and inform him/her that, as indicated in the consent form that she/he had previously signed, our staff are ethically and legally obligated to file a report with Child Protective Services. We have found that this approach conveys respect for the family and mitigates parental anger that might otherwise emanate from filing a report. In our experience, when situations requiring filing a maltreatment report are handled sensitively and framed as stemming from concern for the welfare of the entire family, caregivers often perceive the process as being helpful to them.

Finally, while it is not possible to control what participants do outside of group settings (e.g., Family Forum), we will thoroughly explain the concept and importance of confidentiality and give real life examples of what is appropriate and inappropriate to discuss with people outside of the project. The Peer Moderators will emphasize the importance of confidentiality and will monitor and remind families of this rule and expectation. Privacy settings within the Family Forum will balance participant confidentiality and caregiver preferences. All caregivers will be assigned a unique username to log into the app. They will also be able to select their own username that will show up in the Family Forum. These usernames will be separate from their research participant ID numbers. Participants will be informed of the risks to confidentiality at the outset of the study and will be provided with reminders. Caregivers will have the ability to choose how much information to share about themselves and their experiences in the Family Forum. No other data from other app components will be shared in the Forum, unless the caregiver independently and voluntarily elects to do so.

The FMF Connect intervention is viewed as a “value-added” intervention. Participants can continue to receive care as usual in their community. The alternative to participating in this study is not to participate.

